# PHASE IV TRIAL EVALUATING THE USE OF STEREOTACTIC BODY RADIOTHERAPY FOR THE TREATMENT OF PROSTATE CANCER

## SCHEMA

R	
E	Stereotactic Body Radiotherapy (SBRT)
G	
I	Patient Groups: Prostate Cancer
S	Dose-Fractionation:
T	As monotherapy (No pelvic radiotherapy): 30 – 40 Gy / 4 – 5 fractions
E	After standard pelvic radiotherapy (45 Gy) for higher risk disease: 19 – 21 Gy / 2 – 3 fractions
R	

### **Pelvic Radiotherapy**

Conventionally fractionated external beam pelvic radiotherapy to a dose of 45 Gy in 25 fractions may be given at the discretion of the treating radiation oncologist based on high risk features (i.e. PSA > 20, Gleason score  $\geq 7$ , T3 disease) or high intermediate risk features (i.e. Gleason Score 4 + 3 = 7, PSA > 15).

### **Integrated Boost**

At the discretion of the treating radiation oncologist, an integrated boost of ~ 1 Gy per fraction may be directed at the MR abnormality.

### **Hormone Therapy**

Hormone therapy may be given at the discretion of the patient's urologist and/or radiation oncologist based on high risk features. All forms of androgen suppression including neoadjuvant, concurrent, and adjuvant hormone therapy may be recommended.

### **Radioprotectant**

Rectal amifostine is encouraged but not required and may be given at the discretion of the treating radiation oncologist prior to each fraction. (See 8.1.6)

### **Eligibility**

- Patient age  $\geq 18$  years
- Zubrod performance status of 0-3
- Biopsy-proven prostatic adenocarcinoma, clinical stage T1-3N0M0
- Prostate volume  $\leq 100$  cc
- No prior prostatectomy
- No prior central pelvis radiotherapy except as part of combination therapy for prostate cancer
- No history of scleroderma
- Signed study-specific consent form

## **1.0 Introduction**

Prostate cancer is the most common cancer among American men. The American Cancer Society estimated about 192,280 new cases of prostate cancer in the United States in 2009. Prostate cancer is the second most common cause of cancer-related death with an estimated 27,360 men dying of prostate cancer in 2009. This accounts for 10% of all cancer-related deaths in men. However, with more than 2 million survivors of prostate cancer alive today in the United States, much of the current research focuses not only on improvements in tumor control but also in convenience of treatment delivery and quality of life after treatment. ([www.cancer.org](http://www.cancer.org))

Due to a better understanding of the radiobiology of prostate cancer and the recent advances in precise delivery of radiation therapy, stereotactic hypofractionated radiotherapy is emerging as a new treatment modality with the potential to control organ confined prostate cancer while limiting treatment-related toxicity. The survival of a mammalian cell to radiation damage is classically described by a formalism known as the linear quadratic equation. This mathematical model suggests that the survival rate of an irradiated cell depends on the total radiation dose, the dose per fraction and the overall treatment time. The dose-response of a cell to fractionated radiation is described by the alpha-beta ratio ( $\alpha\beta$ ). A recent review of 17 articles estimated the  $\alpha\beta$  ratio for prostate cancer cells to be 1.85 Gy which suggests that prostate cancer cells have a high sensitivity to fractionation, where higher doses of radiation delivered in fewer fractions would theoretically be advantageous. (1) Stereotactic body radiation therapy (SBRT) is a radiation delivery technique that employs state-of-the-art equipment to position a patient and precisely deliver a high dose of radiation to the treatment volume in a limited number of fractions (usually 5 or less).

Historically, hypofractionated radiation therapy has been reported as early as the 1960's in attempts at the time to improve allocation of resources. Results from a retrospective review of a United Kingdom regimen of hypofractionated radiation therapy using 6 fractions of 6 Gy to a total dose of 36 Gy were found to be comparable to other published outcome data in terms of local tumor control and survival. Early and late toxicity were reportedly within normal limits. (3) Hypofractionation for prostate cancer has more recently moved into several radiation therapy arenas, including external beam radiotherapy, high dose rate brachytherapy and stereotactic radiotherapy. The Radiation Therapy Oncology Group (RTOG) currently has a phase III protocol open to patient accrual comparing conventionally fractionated conformal radiation therapy in 41 fractions of 1.8 Gy (73.8 Gy total) to hypofractionated conformal radiation therapy in 28 fractions of 2.5 Gy (70 Gy total). Other studies have used fraction sizes ranging from 2.5 to 3.1 Gy. (4-7) High dose rate brachytherapy has been used to deliver 5.5 to 11.5 Gy fraction sizes. (8-9).

Recent technological advances have made it possible to deliver high doses of radiation therapy with high precision over just a few days while preserving function of surrounding critical structures. This treatment modality, termed stereotactic body radiotherapy (SBRT), is emerging as an expedient, safe, and effective radiation modality for a variety of malignancies. SBRT was recently defined by the American Society for Therapeutic Radiology and Oncology (ASTRO) as a "treatment method to deliver a high dose of radiation to the target, utilizing either a single dose or a small number of fractions with a high degree of precision within the body" (2). Stereotactic radiotherapy is a well-established treatment for intracranial metastases with local control rates of 80-90%.

Effective biochemical control with low rectal and bladder toxicity has been seen in several recently published clinical studies investigating stereotactic radiation therapy, mainly focusing on the feasibility of using SBRT to treat low-risk prostate cancer. New studies are also emerging that show safety and efficacy in using SBRT in intermediate and high risk prostate cancer patients as a boost after initial conventionally fractionated pelvic irradiation.

The early results of a Canadian phase I/II study (pHART3) using a five-fraction hypofractionated accelerated radiotherapy treatment (35 Gy in five daily fractions) for low risk organ confined prostate cancer were reported by Tang et al. After 6 months of follow up, there was no grade 3 toxicity; however, longer term follow-up is required to assess efficacy and toxicity. (10) Madsen et al. reported on 40 patients treated with SBRT for low risk prostate cancer. They all received 33.5 Gy in five fractions, which is equivalent to 78 Gy in 2 Gy fractions based on alpha/beta ratio of 1.5. The actuarial 4-year biochemical progression-free survival was 90% with a median follow-up of 41 months. There were only two cases of grade 3 acute urinary toxicity. No late toxicity more than grade 3 was reported. (11) King et al. recently reported the Stanford experience of treating 41 low-risk prostate cancer patients with 5 fractions of 7.25 Gy (36.25 Gy) using image-guided SBRT. After a median follow-up of 33 months, they reported no biochemical failure with early and late toxicity profiles no worse than conventional EBRT. In fact, they reported no patients with grade 4 or higher toxicities, only two patients with grade 3 late urinary toxicity and no grade 3 late rectal toxicity. In a separate report, they used the Expanded Prostate Cancer Index Composite (EPIC)-validated quality of life questionnaire to survey 32 consecutive patients treated with SBRT. The mean EPIC sexual domain summary score, sexual function score, and sexual bother score decreased by 45%, 49%, and 25% respectively after 50 months of follow-up. The radiation dose to the penile bulb was not associated with erectile dysfunction. The investigators concluded that the rates of erectile dysfunction appeared comparable to those reported for other modalities of radiotherapy. (12-14)

The results of a phase I dose escalation trial conducted by the University of Texas Southwestern Medical Center were presented at the American Society of Clinical Oncology 2010 Genitourinary Cancers Symposium. Forty-five patients with low to intermediate risk prostate cancer were treated with a 5 fraction SBRT regimen using image guidance, intensity modulation, and a rectal balloon with pretreatment enema. The starting radiation dose was 45 Gy in 5 fractions with subsequent dose escalation to 47.5 Gy and 50 Gy. Patients were followed for toxicity using CTCAE (Common Terminology Criteria for Adverse Events) v3 scoring, as well as AUA (American Urological Association) and EPIC questionnaires. After a median follow-up of 12 months, the investigators observed no grade 3 gastrointestinal toxicities and only one patient with grade 3 genitourinary toxicity. Mean AUA score before SBRT was 5 and during follow-up increased to 8-9. EPIC rectal mean scores were decreased at 6 weeks to 12 months but returned to baseline at 18 months. PSA control was 95% using the nadir-plus-2 definition and 100% using the 3-consecutive-rises definition. Currently, the phase II study that is being conducted utilizes 50 Gy in 5 fractions. (15)

Katz et al. (16) also recently published their results with SBRT for localized prostate cancer. Three hundred and four patients were treated as follows: 50 received 5 fractions of 7 Gy (total dose 35 Gy) and 254 received 5 fractions of 7.25 Gy (total dose 36.25 Gy). Two low risk patients and two high risk patients failed biochemically. However, biopsy revealed both of the low risk patients and one of the high risk patients to be disease free in the prostate gland. In this study, rectal administration of amifostine was given prior to each treatment which likely assisted in keeping toxicity low. In fact, despite higher therapeutic doses based on biological equivalent dose (BED) calculations, the observed rate of acute urinary and rectal toxicity was low, with less than 5% of patients experiencing any acute grade II urinary or rectal toxicity and none experiencing any higher grade toxicity. Late toxicity was also less in the recent study using rectal amifostine when compared to previously published studies. For instance, King et al. reported late grade II urinary toxicity in 24% of patients (33-month follow-up) compared to 2% for the 35 Gy dose level (30-month follow-up) and 5.8% for the 36.25 Gy dose level (11-month follow-up). Regarding late bowel effects, King et al. observed 15% grade II toxicity at 33 month median follow-up. Katz et al. observed a late bowel toxicity rate of 4.2% for grade I toxicity and no higher grade toxicity for the 35 Gy dose level with 30 months of follow-up. They attribute their low bowel toxicity rate to the rectal administration of amifostine prior to SBRT delivery. (12, 16) Amifostine has been reported to significantly reduce the incidence of radiation-induced toxicity in multiple studies and when administered rectally has no related toxicity as opposed to intravenous administration which can cause significant

nausea. In both of these studies, late toxicity rates may increase with more follow-up, but what has been reported thus far is encouraging.

Katz and colleagues also recently reported their preliminary experience with SBRT as a boost for 73 intermediate and high risk prostate cancer patients after initial treatment with 45 Gy conventionally fractionated pelvic irradiation. The 3-fraction SBRT boost dose was escalated from 18 Gy to 19.5 Gy to 21 Gy. After a median follow-up of 33 months, there were less than 7% grade 2 and no higher grade acute toxicities; one grade 3 late toxicity and no grade 4 late toxicities. Of the 97% of patients that had at least 2 years of follow-up, 71.8% achieved a PSA nadir of 0.5 ng/mL. Three-year actuarial biochemical control rates were 89.5% and 77.7% for intermediate and high risk patients, respectively – 3 intermediate risk and 7 high risk patients with biochemical failures. (17)

The University of San Francisco (UCSF) recently published their results with SBRT both as monotherapy and as a boost treatment for prostate cancer. At the time of the study, 38 patients had been treated with a minimum follow-up of 12 months – 20 as monotherapy (9.5 Gy x 4 fractions) and 18 as a boost (9.5 Gy x 2 fractions) after external beam radiotherapy and androgen deprivation therapy. With a median follow-up of 18.3 months, 42% and 11% had acute grade 2 genitourinary and gastrointestinal toxicity, respectively, with no grade 3 or higher acute toxicity. Two patients experienced late grade 3 genitourinary toxicity. All patients were free of biochemical or clinical recurrence at the time of follow-up with a median PSA nadir of 0.35 ng/mL. (18)

The UCSF authors drew upon their experience with high dose rate (HDR) brachytherapy in which they were able to achieve similar dosimetry when compared with SBRT. Hypofractionation with HDR brachytherapy has demonstrated excellent efficacy and toxicity profiles as both monotherapy and after external beam radiotherapy as a boost for organ confined prostate cancer. The UCSF has recently reported its experience with HDR brachytherapy boost in mostly intermediate and high risk disease in which they achieved 5-year bNED (biochemical no evidence of disease) rates of 93% with minimal toxicity. (19) Superior bNED rates have also been reported in a randomized Phase III trial of HDR brachytherapy boost compared with external beam radiotherapy (EBRT) alone. (20) In addition, a systematic review of the literature recently concluded that the combination of EBRT and HDR brachytherapy results in superior bNED rates and overall survival when compared with EBRT alone or EBRT with a permanent prostate seed implant boost. (21) Grills and colleagues at William Beaumont Hospital have reported their HDR brachytherapy experience. Compared with permanent prostate seed implant with low dose rate palladium seeds, HDR brachytherapy was not only able to achieve equivalent biochemical control, but was also associated with decreased rates of acute and late toxicity and improved quality of life measures. (22) Using the HDR brachytherapy dose and fractionation, SBRT could theoretically achieve the excellent therapeutic profile of HDR brachytherapy while avoiding the risks of an invasive procedure and its inherent logistical challenges.

SBRT for prostate cancer appears to be effective in controlling disease with acceptable toxicity. However, more studies are needed with longer term follow-up. St. John's Mercy has installed an Elekta Synergy-S® linear accelerator at the David C. Pratt Cancer Center that is specifically designed to deliver highly-precise SBRT treatments. It has a tightened isocenter accuracy calibrated to a precision of within 1.5 mm diameter, a micro-MLC for treatment of small radiation ports, a specially designed Hexapod® table top that can correct for patient misalignment in both translational and rotational directions, an onboard cone-beam kV CT for precise tumor localization immediately prior to treatment, and four-dimensional CT (4D-CT) which together allow for accurate monitoring of and compensation for tumor motion during respiration, active breathing control for respiratory gating, and real-time continuous fluoroscopic capability for visual confirmation that the target remains in the treatment field.

## **2.0 Objectives**

This study will evaluate the local control rate as well as acute and late toxicity rates of stereotactic body radiotherapy (SBRT) for the treatment of organ confined prostate cancer.

### **2.1 Hypothesis**

- 2.1.1 For selected patients with localized prostate cancer (clinical stage T1-2N0M0), stereotactic body radiotherapy (SBRT) is technically feasible with acceptable complication rates.
- 2.1.2 Biochemical control with stereotactic body radiotherapy (SBRT) will be at least as good as standard fractionation radiation therapy

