### **2.2 Study Design**

- 2.2.1 Single site, non-randomized, prospective, phase IV trial
- 2.2.2 Study group will include organ confined prostate cancer
- 2.2.3 Data collected will include patient demographics, pathology data, tumor stage, SBRT dose fractionation scheme, dose received by adjacent critical normal tissues, tumor recurrence data, and acute and late toxicities.
- 2.2.4 Follow up data will be collected during the patient's standard office visits. The anticipated duration of this study is 5 years

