### **2.3 End Points**

- 2.3.1 Primary endpoints will be biochemical control rate
  - Serial blood tests for prostate specific antigen (PSA) levels will be obtained at regular intervals
  - The "Phoenix definition" for biochemical recurrence (nadir + 2 ng/ml) will be used
- 2.3.2 Secondary endpoint will be late toxicity rate.
  - Grading of acute and late complications is defined in Section 12.3 (Appendix III)

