**10.0 Patient Assessment**

**10.1 Study Parameters**

The following are suggested patient follow-up intervals and evaluations that may be performed to either assess for treatment toxicity or tumor response to SBRT:

Assessment	Pre-Rx	Post-Rx 6 wk	Post-Rx 3 mo	Post-Rx 6 mo	Post-Rx 9 mo	Post-Rx 1 yr
H&P / Weight	X	X	X	X	X	X b
Disease status	X	X	X	X	X	X b
AUA/EPIC Questionnaire	X	X	X	X	X	X
Toxicity Assessment		X	X	X	X	X b
PSA	X	X	X	X	X	X

AST/ ALT / Alk Phos	X a					
Total Bilirubin	X a					
PT/ PTT	X a					
Creatinine	X a					
CBC with Platelets	X					
Bone scan	X a					
CT/MR abdomen/pelvis	X					X b

- a. if clinically appropriate  
b. at the discretion of the treating radiation oncologist

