## **10.2 Response Evaluation**

### **10.2.1 Prostate Specific Antigen (PSA)**

- Will be obtained every 3 months for the first 2 years, then as indicated at the discretion of the treating physician.
- Biochemical failure defined as nadir + 2 ng/ml
- Repeat imaging including abdominopelvic CT scan, MRI, or bone scan as clinically indicated.

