### **11.5 Statistical Analysis**

**11.5.1** The overall survival and biochemical control rates will be analyzed.

**11.5.2** The incidence rate for any serious adverse events will be calculated.

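### Section 2.1.2 claims parity or better against standard fractionation, but the SBRT-only design fixes no reference rate, margin, time point or decision rule by which to judge it

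*Combined protocol and SAP*

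**What the plan says.** The only efficacy hypothesis is Section 2.1.2: "Biochemical control with stereotactic body radiotherapy (SBRT) will be at least as good as standard fractionation radiation therapy". Section 2.2.1 describes the study as a "Single site, non-randomized, prospective, phase IV trial", and the Schema registers patients to SBRT only, as monotherapy or after pelvic radiotherapy.

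Section 2.3.1 sets the endpoint: "Primary endpoints will be biochemical control rate". It defines failure by the Phoenix rule (nadir + 2 ng/ml), which Section 10.2.1 repeats. It gives no time at which the rate is to be read.

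The whole efficacy analysis plan is Section 11.5.1: "The overall survival and biochemical control rates will be analyzed". Section 11.5.2 adds only an incidence rate for serious adverse events.

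On follow-up, Section 10.2.1 says of PSA: "Will be obtained every 3 months for the first 2 years, then as indicated at the discretion of the treating physician". Section 10.1 introduces its visit table more loosely ("The following are suggested patient follow-up intervals and evaluations that may be performed"), and the table's columns end at 1 year. Section 2.2.4 adds: "The anticipated duration of this study is 5 years". None of these is named as the evaluation time for the primary endpoint.

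**The concern.** A claim of being no worse than another treatment can be judged only against a stated reference, by a stated margin, at a stated time and by a stated rule. Section 2.1.2 makes such a claim on the primary endpoint, and the rest of the plan supplies none of these elements.

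The verdict on the trial's one efficacy hypothesis would then depend on which published series is taken as the benchmark, what shortfall is tolerated and when control is read. All of these could be settled after the results are known. Case mix adds to the freedom of choice: Section 3.1.3 admits T1 to T3 disease, and pelvic radiotherapy (Schema) and hormone therapy (Section 9.1) are discretionary, so a published series can be found that looks more or less favourable than the enrolled patients.

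**Working it through.** The plan has no sample size, power or benchmark figure to reproduce. The check has three steps.

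**1. What the claim needs, and what the plan gives.**

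| Element | In the documents |
|---|---|
| Comparator | A treatment class only (2.1.2). Section 1.0 mentions one conventional regimen, 41 × 1.8 Gy = 73.8 Gy, as an arm of another trial, not as the benchmark |
| Reference cohort or dataset | Not stated |
| Reference rate | Not stated |
| Margin | Not stated |
| Evaluation time | Not stated |
| Decision rule, alpha or CI criterion | Not stated |
| Planned number of patients | Not stated |
| Failure definition | Stated: nadir + 2 ng/ml (2.3.1, 10.2.1) |

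**2. Whether Section 1.0 supplies a reference rate indirectly.** It does not. The numerical biochemical control rates there are:
- 90% at 4 years (low-risk SBRT series of 40 patients)
- 95% by nadir + 2 (SBRT dose-escalation trial, median follow-up 12 months)
- 89.5% and 77.7% at 3 years (SBRT boost series, intermediate and high risk)
- 93% at 5 years (HDR brachytherapy boost)

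The other SBRT series are given as counts of failures or as none. Where external beam radiotherapy alone appears, the HDR combination is called superior without a figure. One SBRT schedule is converted to an equivalent dose in 2 Gy fractions, but that is a dose, not a control rate.

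**3. Whether the missing choices could change the verdict.** All inputs here are assumed: an observed control proportion of 90%, a benchmark of 90%, and margins of 5 or 10 points. Control is treated as binary with no censoring.

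The exact (Clopper-Pearson) 95% limits for x of n are
- lower = Beta quantile(0.025; x, n − x + 1)
- upper = Beta quantile(0.975; x + 1, n − x)

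The claim is met if the lower limit exceeds benchmark − margin: 90 − 10 = 80%, or 90 − 5 = 85%.

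| x/n | 95% CI | 10-point margin (> 80%) | 5-point margin (> 85%) |
|---|---|---|---|
| 45/50 | 78.2–96.7% | fails | fails |
| 90/100 | 82.4–95.1% | meets | fails |
| 180/200 | 84.98–93.8% | meets | fails, just |

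At n = 100 the same data give opposite answers under two margins, and the plan chooses neither.

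The number of patients needed shows the same dependence. Take an exact one-sided binomial test of H0: p ≤ benchmark − margin, with true p equal to the benchmark, alpha 0.025 and power at least 80%. With a 90% benchmark, n is 356, 107 or 54 for margins of 5, 10 or 15 points. Over benchmarks of 80% to 93% and the same margins, n runs from 44 (93%, 15 points) to 553 (80%, 5 points). These are not proposed sample sizes. They show how much is left open.

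**The case against.** The best defence is that the study is descriptive. Section 2.0 speaks of evaluating rates, Section 11.5 plans no test, and in a non-randomized phase IV study 2.1.2 can be read as a motivating expectation. Much of this stands, and it limits the consequence to one claim and one undefined estimate. It does not rescue the wording: if the study is descriptive, its hypothesis should not assert parity on the primary endpoint. Section 11.4 also appeals to equivalent or better tumour control as part of the rationale.

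Several stronger readings are tempting, and the documents do not support them.

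- *That there is no comparator at all.* A class is named. What is missing is a reference cohort and rate.
- *That a single-arm trial could never address the question.* It could support a weaker historical comparison if benchmark, margin and time were fixed beforehand. Here they are not.
- *That the evaluation time is implicitly 2 or 5 years.* Two years is where scheduled PSA testing ends, and 5 years is the anticipated length of the study. Neither is tied to the endpoint.
- *That the choice of landmark alone moves the verdict by several points.* Under a constant hazard, 90% at 4 years becomes 0.90^(2/4) = 94.9% at 2 years, and 77.7% at 3 years becomes 0.777^(2/3) = 84.5%. These are SBRT rates only. A comparator read at the same time would move too, so the shifts matter only if the two are read at different times.

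**Conclusion.** The point holds in limited form. Section 2.1.2 makes a non-inferiority-type claim that the design as written cannot support, because nothing fixed in advance says what SBRT is compared with, by how much it may fall short, when, or by what rule. The biochemical control rate in 2.3.1 and 11.5.1 is also not a defined quantity without a time point.

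The documents give no figure from which to size the effect on the conclusion. The illustration rests on an assumed 90% benchmark, an assumed 90% observed rate and complete binary follow-up. On those inputs, 100 patients would pass at a 10-point margin and fail at 5. Censoring would widen the intervals.

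A reader might infer that the trial is underpowered or that its data would be uninterpretable. Neither follows. No sample size is stated against which power could be judged, and the failure definition and the 3-monthly PSA schedule to 2 years give a sound basis for estimation. The change should be made, but it concerns what the trial may claim rather than whether it can be run.

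**What to change.** - **Section 2.1.2:** delete the comparative wording and state the aim as estimating freedom from biochemical failure after SBRT.
- **Section 11.5.1:** specify a Kaplan-Meier estimate of freedom from biochemical failure (nadir + 2 ng/ml) with a 95% CI, and keep overall survival as a separate analysis.
- **Time origin and landmark:** state the origin, and fix and justify the landmark before analysis. Two years is the natural candidate because scheduled PSA testing ends there in Section 10.2.1. Report later estimates with their uncertainty, since later PSA testing is discretionary and Section 1.0 itself asks for longer follow-up.
- **Intercurrent events:** say how death without biochemical failure is handled, and how treatment for recurrence is handled. Appendix VIII already records both with dates.
- **Treatment groups:** report monotherapy and boost separately and descriptively, and tabulate hormone therapy use.
- **External comparison:** describe any comparison with published standard-fractionation rates as historical and descriptive, not as non-inferiority.

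The cost is mainly redrafting two short sections. The downsides are real. The efficacy claim becomes more modest. Subgroup estimates may be imprecise: 18 of 20 controlled, for example, has an exact 95% CI of 68.3% to 98.8%. A 2-year value may also partly reflect androgen suppression, because all forms of hormone therapy are permitted; tabulating its use shows this but does not remove it.
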